7.10 Safety Evaluation

Additional summaries of safety will be assessed for the FAS population. These include summaries of adverse events and device deficiencies (DD). AEs and DDs will be summarized with number of events, number of subjects who experienced the event, and percentage of subjects who experienced one or more events.

AEs for all subjects will be collected from consent through the study exit. AEs and DDs will be coded and summarized using the most recent version of Medical Dictionary for Regulatory Affairs (MedDRA). Serious Adverse Events (SAE), deaths, and Surgical Site Events (SSEs) will be adjudicated by an independent CEC as defined in the CIP. Cases where the investigator's classification does not match CEC's adjudication classification, both determinations will be provided within the final report; however, the CEC's adjudication will be used for data analysis.

AEs occurring in subjects excluded from the FAS will be followed post-consent through study exit and will be reported in the CSR. These AEs will not be included in the FAS summary analysis for either AE reporting or the analysis of the primary and secondary endpoints.

For the FAS, AEs will be reported by the type (preferred term), seriousness, and procedure/device relatedness. Summaries will focus on the time periods which are complete as of the snapshot for the report, with special attention to those periods which start during the procedure (e.g. during the procedure to 30 days after the procedure).

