Study Procedures and Assessments	
Screening, Surgical Procedure, Hospital Discharge, and Post-Discharge Follow-Up at 30 days (<math>\pm 7</math> days), 3 months (<math>\pm 14</math> days), 1 year (<math>\pm 30</math> days) and 2 years (<math>\pm 30</math> days):
 
Screening: To determine study eligibility and collect baseline information (i.e., demographics, medications, medical history, surgical history)
 
Surgical Procedure: To re-confirm eligibility criteria, procedure set-up and take-down, medication changes, interoperative complication evaluation, disease state evaluation, procedure success, conversion, adverse event evaluation, device deficiency evaluation
 
Up to Hospital Discharge: Adverse event evaluation, subject complication rate, disease state evaluation, protocol deviation and medications.
 
Post-Discharge Follow-Up: Adverse event evaluation, subject complication rate, disease state evaluation, length of hospital stay, readmission (if applicable), reoperation (if applicable), recurrence (if applicable), chronic pain, protocol deviation, medications, and study exit.

Safety Assessments	
Data on the presence of adverse events (AEs) will be collected from the time of consent. Safety assessments will be based on the full analysis set (FAS). Data including AE term, incidence, severity, and procedure/device relatedness will be reported. AEs for all FAS subjects will be collected from time of consent through the study exit.
 
AEs will be assessed by the Investigator and the sponsor. All Serious Adverse Events (SAE), deaths, and Surgical Site Events (SSEs) will be adjudicated by an external, independent Clinical Events Committee (CEC).
 
AEs occurring in subjects excluded from the full analysis set will be followed post-consent through study exit and will be reported in a listing in the clinical study report (CSR). These AEs will not be included in the FAS summary for either AE reporting or the analysis of the primary and secondary endpoints.
 
AEs and Device Deficiencies will be summarized in tables displaying the

*Medtronic Business Restricted*

	number of events, and the number and percentage of subjects with events.

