## 12 Adverse Events and Device Deficiencies

### 12.1 Adverse Events

All AEs, including non-subject AEs, will be collected throughout a subject's participation, starting from the time the informed consent form is signed, through 30 days after the day of the procedure, regardless of their severity, relationship to the Hugo™ RAS system or study procedures.

After 30 days, all AEs will be assessed by the surgeon and those AEs deemed attributable to the procedure and / or study device will be reported. All deaths will be collected throughout a subject's participation, regardless of relatedness.

Reporting of these events to Medtronic will occur on an AE Form, including event description, date of AE, treatment, resolution, assessment of both the seriousness of the AE and the relatedness to the study device, procedure. Each AE must be recorded on a separate AE eCRF.

AE definitions used in this study (**Table 8**) are based on ISO 14155:2020 (Clinical Investigation of Medical Devices for Human Subjects – Good Clinical Practice). Documented pre-existing conditions are not considered AEs unless the nature or severity of the condition has worsened. See **Section 14** for details regarding AE analyses in each study analysis set. In addition, AEs impacting users or other persons (non-subject AEs) will be collected on a non-subject AE CRF.

Any unresolved procedural or device-related events that are still ongoing past study exit will be monitored by the Investigator per their institutional standard-of-care.

Unavoidable adverse events (UAE) (those that are inherent to the procedure and are expected to occur in all subjects for an expected duration) listed in **Table 11** will not be captured or reported unless the adverse event worsens or persists outside the stated timeframe post procedure. **Section 11.1** includes a list of several but not all-encompassing anticipated adverse events.

All Serious Adverse Events (SAE), deaths, and Surgical Site Events (SSEs) will be adjudicated by an independent CEC through 30 days post-procedure as of revision 5.0 of the protocol.

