## 12.4 Definitions/Classifications

This study is not within the scope of ISO 14155:2020 but will use AE definitions according to ISO 14155:2020 for consistency in reporting.

This study will collect the following:

- All adverse events, including non-subject AEs, from the time the informed consent is signed through the first 30 days after the day of the procedure, regardless of their severity, relationship to the Hugo™ RAS system or study procedures. After 30 days, all AEs will be assessed by the surgeon and those AEs deemed attributable to the procedure and/or study device will be reported. All deaths will be collected throughout a subject's participation, regardless of relatedness.
- All device deficiencies (all components of the Hugo™ RAS system)

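### SAP 7.10 and the protocol synopsis omit the day-30 limit on AE collection, so any all-cause AE or SAE total carried past day 30 would mix two collection rules and undercount unrelated non-fatal events

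*SAP*

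**What the plan says.** SAP 7.10 gives the collection window with no limit by relatedness: "AEs for all subjects will be collected from consent through the study exit". It then plans the tables: "For the FAS, AEs will be reported by the type (preferred term), seriousness, and procedure/device relatedness", with numbers of events, numbers of subjects and percentages. On timing it says "Summaries will focus on the time periods which are complete as of the snapshot for the report, with special attention to those periods which start"; the sentence goes on to name a start at surgery, with procedure to day 30 as its example. SAP 7.2 plans a final report after the 2-year follow-up.

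The protocol synopsis (Safety Assessments) is equally unrestricted: "AEs for all FAS subjects will be collected from time of consent through the study exit".

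Protocol 12.1 sets two rules. All AEs are collected from consent "through 30 days after the day of the procedure, regardless of their severity, relationship to the Hugo™ RAS system or study procedures". After day 30 the surgeon assesses AEs and "those AEs deemed attributable to the procedure and / or study device will be reported". Section 12.4 repeats both rules. The one stated exception is fatal events: "All deaths will be collected throughout a subject's participation, regardless of relatedness". Neither section exempts non-fatal SAEs.

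Two other places bear on this:

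- Protocol 14.15 describes collection up to exit but ties it to 12.1 and 12.2.
- The SAE row of protocol Table 10 (section 12.5.2) sets a deadline for reporting serious events to the sponsor. It refers to all of them, with no day-30 limit.

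**The concern.** A programmer working from SAP 7.10 would take the AE dataset to be all-cause for the whole of follow-up. Under protocol 12.1 it is all-cause only to day 30. A cumulative table at 2 years by preferred term, seriousness and relatedness would then hold three kinds of data: every event to day 30, only surgeon-attributed non-fatal events afterwards, and all deaths throughout.

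Three readings of such a table would be wrong:

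- The percentage of subjects with any SAE would look all-cause and be too low.
- The share of events classed as related would be too high.
- Part of the apparent fall in event frequency after day 30 would come from the collection rule.

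Nothing in the table would show the reader that unrelated events were not collected.

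**Working it through.** The plan states no figure to reproduce. The check is a comparison of texts, followed by arithmetic for scale.

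**1. Collection rule by place**

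| Place | To day 30 | After day 30 |
|---|---|---|
| SAP 7.10 | all AEs | all AEs |
| Protocol synopsis | all AEs | all AEs |
| Protocol 12.1, 12.4 | all AEs | related AEs and all deaths |
| Protocol 14.15 | as 12.1 | as 12.1 |
| Protocol Table 10, SAE row | all SAEs | no limit stated |

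The SAP sentence carries no cross-reference to 12.1, and SAP 7.11 reports no change from protocol version 5.0.

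**2. Outputs that cross the day-30 boundary**

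- Primary safety endpoint and 30-day secondary endpoints: these end at day 30. Not affected.
- Device- or procedure-related AEs to 2 years (SAP 7.9.4): related events are collected on both sides of day 30. Not affected.
- Deaths: all-cause throughout. Not affected.
- All-cause AE or SAE counts or percentages, or a related/unrelated split, beyond day 30: two rules in one table. Affected.

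**3. Direction of the error.** Let R be related events to 2 years, U1 unrelated events to day 30, and U2 unrelated non-fatal events after day 30. Under 12.1 the table shows a total of R + U1 in place of R + U1 + U2. It shows a related share of R/(R + U1) in place of R/(R + U1 + U2). Whenever U2 > 0 the total is too low; if R > 0 as well, the related share is too high.

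**4. Time under each rule.** Inputs are 730 days of follow-up (SAP 7.2) and 192 treated subjects (SAP 6), with full retention assumed.

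- All-cause: 30/730 = 4.1% of follow-up; 192 × 30/365 = 15.8 person-years.
- Related-only plus deaths: 700/730 = 95.9%; 192 × 700/365 = 368.2 person-years.

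**5. Illustration.** The documents give no background rate, so the rates below are assumptions. They are taken as constant, with no unrelated non-fatal SAE captured after day 30. Events = rate × person-years. Subjects with at least one = 1 − exp(−rate × years).

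| Assumed unrelated non-fatal SAEs per person-year | Recorded to day 30 | Unrecorded, days 31–730 | Subjects with one or more, 2 years | Subjects with one or more, 30 days |
|---|---|---|---|---|
| 0.02 | 0.3 | 7.4 | 3.9% | 0.2% |
| 0.05 | 0.8 | 18.4 | 9.5% | 0.4% |
| 0.10 | 1.6 | 36.8 | 18.1% | 0.8% |
| 0.20 | 3.2 | 73.6 | 33.0% | 1.6% |

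The last column is what a 2-year table could show for unrelated SAEs under the 12.1 rule.

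**The case against.** The strongest reply is that the plan never promises the table that would go wrong. SAP 7.10 puts its emphasis on complete periods such as procedure to day 30. SAP section 3 makes the planned analyses the basis of the 30-day report. The only AE outcome named through 2 years is restricted to related events, which matches the later collection rule. This stands in part: the understatement arises only if an all-cause table past day 30 is produced. But an emphasis is not a limit. At the 2-year data cut the 2-year period is complete in the SAP's own terms, protocol 14.2 includes all available data, and no section stops all-cause tables at day 30 or splits them there.

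A reader might infer that every AE table running past day 30 is affected. The documents do not support that, because related-only tables and all-cause deaths each follow one rule throughout. Nor does protocol 14.15 share the omission, since it refers back to 12.1.

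It can also be said that unrelated SAEs may not all be lost. If the Table 10 row is meant to reach beyond day 30, they would be reported. Table 8 also counts possible relationships as related, including cases that cannot be assessed, so some background events would be kept. Both points stand. Table 10 mainly sets deadlines, so its scope is unclear, and the counts above are illustrations under stated assumptions.

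**Conclusion.** The conflict is real. SAP 7.10 and the protocol synopsis describe unrestricted collection to exit, while protocol 12.1 and 12.4 restrict non-fatal AEs after day 30 to those attributed to the procedure or device. The scope of the Table 10 SAE row is unresolved. Any all-cause AE or SAE count, percentage or relatedness split carried past day 30 would understate unrelated non-fatal events.

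The consequence is conditional on such a table being produced, and it is confined to descriptive safety summaries. The direction follows from the collection rule. The size does not: it depends on an unstated background rate, on retention and on how Table 10 is read. The firm figure is that the related-only rule governs 700 of 730 planned days, or 95.9%.

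**What to change.** 1. In SAP 7.10 and the protocol synopsis, replace the unrestricted sentence with the rule in protocol 12.1/12.4, or cross-refer to it. Protocol 14.15 already does so.
2. State whether the Table 10 SAE row sets a deadline only for events within the 12.1 scope or requires all SAEs until exit. If it requires all SAEs, 12.1 and 12.4 must say so. The SAE undercount would then fall away, but the one for non-serious AEs would remain.
3. Under the 12.1/12.4 rule, stop all-cause AE and SAE tables at day 30. Show or list AEs between consent and incision separately, so that they keep a stated place.
4. Present later periods in tables labelled as procedure- and/or device-related AEs only, with all-cause deaths in their own row. Add a note that event-committee adjudication also ends at day 30 (protocol 12.1 and 13.1), so later relatedness rests on the site's assessment.

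The cost is a few sentences and one table split, with no new data. The final report would have no single all-cause AE or SAE rate through 2 years, but data collected under 12.1 could not support one.

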7.11 Changes to Planned Analysis

There were no changes to the statistical analysis as compared to CIP V5.0.

-

8. Validation Requirements

The analysis of the primary objectives will be validated by Level I, in which the peer reviewer independently programs output and then compares the output with that generated by the original Statistical Programmer. The analysis of the secondary and ancillary objectives, as well as the main AE/PD summaries will be validated by at least Level II, in which the peer reviewer reviews the code; where appropriate, performs manual calculations or simple programming checks to verify the output.

9. References

Holm, S. (1979). A Simple Sequentially Rejective Multiple Test Procedure. *Scandinavian Journal of Statistics*, 6, 65-70.

Rubin DB. *Multiple Imputation for Nonresponse in Surveys*. New York: John Wiley and Sons; 2004.
